**Variables will be collected to establish different patterns of response to treatment and evolution of LN:**

- a) complete renal response, defined according to EULAR/ERA-EDTA recommendations (13): proteinuria  $<0.5$  g/24 hours and (near) normal estimated GFR.
- b) partial renal response, defined according to EULAR/ERA-EDTA recommendations (13):  $\geq 50\%$  proteinuria reduction to subnephrotic levels and (near) normal eGFR
- c) no response: all the other cases.
- d) proteinuria levels at 12 months of treatment,
- e) renal relapse as defined as reproducible increase in uPCR to  $>1$  g if the baseline value was  $<0.2$  g, to  $>2$  g if the baseline value was between  $0.2$  g and  $1$  g, or more than twice the value at baseline if the baseline value was  $>1$  g AND/OR reproducible decrease in GFR of  $>20\%$ , accompanied by proteinuria ( $>1$  g), and/or RBC and/or WBC cellular casts (yes/no and number of flares), e) time to first flare, f) chronic renal failure,
- f) end-stage renal disease requiring dialysis and/or renal transplantation.

Data collection will be based on the clinical history of the patients included in the study.

Confidentiality will be respected in accordance with RD 1720/2007 and the Data Protection Laws. Approval will be requested from the **Galician Clinical Research Ethics Committee (CEIC)** as well as from the CEIC of each center, if necessary.

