## **PATIENTS AND METHODS**

### **Inclusion criteria:**

Patients with a diagnosis of SLE according to the 1997 American College of Rheumatology (ACR) criteria (8).

Diagnosis of lupus nephritis type 3,4,5 or mixed forms of the above according to the International Society of Nephrology (ISN)/Renal Pathology Society (RPS) classification of LN (9).

Date of performance of the renal biopsy: year 2000 or later. The reason for this time frame is the theoretical homogenization in the therapeutic management of LN with the introduction of MMF into the therapeutic armamentarium of LN and the extension of the use of the European intravenous cyclophosphamide guideline.

Availability of the patient's first renal biopsy specimen preserved for re-evaluation.

Availability of essential clinical data to carry out the study.

Signature of the informed consent by the patient.

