#### Exclusion criteria:

Refusal by the patient to sign the informed consent.

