## **STATISTICAL ANALYSIS**

In the descriptive study, numerical variables will be expressed as mean  $\pm$  standard deviation (SD) or median and interquartile range (IQR), depending on whether the distribution is normal or not, respectively. We will establish 2 groups of patients, according to the response to treatment and the clinical evolution of the patient with LN (i.e., complete remission yes/no). To establish differences between patients in these 2 groups, we will use the  $\chi^2$  test for categorical variables or Fisher's exact test when the expected frequencies are small, the t-Student test for normal continuous variables, and the Mann-Whitney U test for variables with non-normal distribution.

Different methods to analyze and/or mitigate the missing data problem will be used.

The percentage of positive cells and staining intensity will be correlated with the different patterns of response to treatment and evolution of LN.

Univariate and multivariate linear logistic regression analyses will be performed to explore the relationships between the different variables studied (clinical, histopathological, therapeutic...) and the presence of the different renal outcomes (dependent variable). Values of  $p < 0.05$  will be considered significant.

We will carry out other different statistical methods according to the results that we observe from our initial analysis.

Statistical analyses will be performed by the Statistical Specialist of the IRIDIS Group.

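### Complete response is an absolute level and entry sets no baseline proteinuria or eGFR requirement, so a patient already at that level at LN diagnosis can count as a responder whatever the treatment did

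*Combined protocol and SAP*

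**What the plan says.** **Entry.** Under Inclusion criteria the renal requirement is histological: "Diagnosis of lupus nephritis type 3,4,5 or mixed forms of the above". The other entry conditions are an SLE diagnosis, a biopsy from 2000 onward, "Availability of the patient's first renal biopsy specimen preserved for re-evaluation", "Availability of essential clinical data to carry out the study" and consent. The only exclusion is "Refusal by the patient to sign the informed consent". No value of proteinuria or eGFR is required at biopsy.

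**Outcomes.** In the list of response patterns under Methods, item a) is "complete renal response, defined according to EULAR/ERA-EDTA recommendations (13): proteinuria" below 0.5 "g/24 hours and (near) normal estimated GFR". Item b), partial response, needs at least a 50% "proteinuria reduction to subnephrotic levels and (near) normal eGFR". Item c), no response, takes everyone else. Chronic renal failure and end-stage renal disease are listed without a date or a new-onset condition.

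**Analysis.** Statistical analysis forms two groups, with complete remission (yes/no) as the named example. It then plans logistic regressions for "the presence of the different renal outcomes (dependent variable").

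**Data.** Creatinine, GFR and proteinuria are collected at LN diagnosis and at last evaluation (general variables, Methods). Nothing in the plan uses the baseline values to decide who is analysed for which outcome.

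**The concern.** Partial response is measured against the patient's own baseline. Complete response, which defines the main groups, is not. Take a class 3 patient biopsied with 0.4 g/24 h and normal eGFR. Item a) is met on the day of biopsy, and if nothing changes the patient is classed as a complete responder. That classification carries no information about treatment.

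This matters because the stated objective is to predict the response to the different drugs from tissue markers. Experimental strategy and rationale says that expression of BLYS and its receptors is associated with progression and severity, and that plasma cell infiltration goes with more severe nephritis. Patients who are responders because their disease was mild at biopsy may well have different marker levels for that reason alone. Part of the comparison would then measure severity at biopsy instead of response.

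**Working it through.** **1. Can the rule be met at baseline?** Each place that could prevent it was checked.

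| Place | Baseline condition |
|---|---|
| Inclusion criteria | Histological class only; clinical data must exist, but no value is required |
| Exclusion criteria | None |
| Complete response | Absolute level, no change required |
| Partial response | At least 50% reduction from baseline |
| No response | Residual group; no not-at-risk category |
| Statistical analysis | No restriction to patients at risk; no commitment to adjust for baseline proteinuria or eGFR |

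Nothing prevents it. Complete remission in Statistical analysis is taken here to mean complete renal response as defined in Methods.

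**2. Plan's own figure.** The target of about 60 biopsies has no effect size, response rate or power behind it, so there is nothing to reproduce. All rates below are assumptions, used only to show size.

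**3. Spurious association.** Assume 60 patients, no true marker effect, 45% complete response among those at risk, and a share f already in complete response whose marker is lower by d SD. The fraction of responders who were responders from the start is f / (f + (1 − f) × 0.45), and the expected spurious difference is d times that fraction. With d = 1:

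- f = 10%: 0.10 / (0.10 + 0.405) = 0.20 SD
- f = 15%: 0.15 / (0.15 + 0.3825) = 0.28 SD
- f = 20%: 0.20 / (0.20 + 0.36) = 0.36 SD

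Simulated Mann-Whitney rejection rates at 0.05 are below. Ranges are over repeat runs, most of 3,000 or 4,000 simulated studies.

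| Share already in response | Patients of 60 | 1 SD shift |
|---|---|---|
| 5% | 3 | about 6% (5.9-7.1%) |
| 10% | 6 | 9.3-9.7% |
| 15% | 9 | 15.7-17.0% |
| 20% | 12 | 21.9-23.2% |

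With a 0.5 SD shift the rate is 5-9% over these shares. Restricting the analysis to patients at risk brought it back to 4.4-5.4% in every scenario.

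**4. Same effect with a binary marker.** Take 30 marker-high and 30 marker-low patients, with 50% response among those at risk in both groups and a share s already in response in the marker-low group only. The marker-low rate becomes s + (1 − s) × 0.5.

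- s = 10%: 0.55, odds ratio 0.55/0.45 = 1.22, chance of p < 0.05 7%
- s = 20%: 0.60, odds ratio 0.60/0.40 = 1.50, chance 12%
- s = 30%: 0.65, odds ratio 0.65/0.35 = 1.86, chance 21%

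**5. Dilution.** If the share is equal in both marker groups, a real effect shrinks. Assume 35% versus 70% response among those at risk, 30 per group, two-sided 0.05, normal approximation. Each rate p becomes s + (1 − s)p, so the difference becomes (1 − s) × 0.35.

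| s | Difference, all patients | Power, all patients | Power, at-risk only |
|---|---|---|---|
| 0 | 0.35 | 79% | 79% |
| 5% | 0.333 | 75% | 77% |
| 10% | 0.315 | 70% | 74% |
| 20% | 0.28 | 61% | 69% |

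In this setting the restricted analysis has more power despite fewer patients.

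**6. Does baseline adjustment help?** Patients already in response were simulated as those with the lowest values of a continuous baseline variable, with a 1 SD shift. Adding that variable to a logistic model cut rejection from 15.2% to 9.5% at a 15% share, and from 21.1% to 10.6% at 20%. The part of the excess over 5% that is removed is 5.7/10.2 = 56% and 10.5/16.1 = 65%.

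**The case against.** **Intent.** The outcome list is headed as response to treatment and evolution, which suggests that the authors mean events after biopsy and that a response needs something to respond from. That is a fair reading of intent, but no rule enforces it and item a) applied as written gives the result above.

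**Size.** In class 3-5 disease on a first biopsy, proteinuria below 0.5 g/24 h with near-normal eGFR may be uncommon. The larger false-positive rates need 9 to 12 of 60 patients and a full 1 SD shift, neither of which comes from the documents. At a 5% share or a 0.5 SD shift the inflation is minor. This stands, and it limits the claim. The study is also a proof of concept with exploratory regressions.

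**Stronger readings that the documents do not support.**

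- A reader might infer that the plan counts renal failure already present at biopsy as an outcome, because the regression models the presence of outcomes. In a logistic model that word ordinarily means occurred or not. A new-onset qualifier is missing, but there is no rule to count prevalent cases, and renal status is recorded separately at diagnosis and at last evaluation.
- A reader might infer that adjusting for baseline proteinuria or eGFR is useless here. In the calculation above it removed more than half of the excess. It is a partial remedy, and the plan does not commit to it.
- A reader might infer that excluding patients already in response settles the matter. It does not: a patient with fixed eGFR loss at biopsy can meet neither response definition and remains a certain non-responder.

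**Conclusion.** The point holds for complete response. As written, a patient who meets the definition at LN diagnosis and stays there is a complete responder in the main comparison, and the plan has no category for patients not at risk. The bias can run either way: a false association if these patients differ in marker level, or dilution if they do not.

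Its size is unknown because the documents give neither the share nor the marker difference. Under the assumptions stated (60 patients, 45% response among those at risk, 1 SD shift), the false-positive rate runs from about 6% at a 5% share to 22-23% at 20%. The change should be made because it is cheap and because reporting the number set aside reveals the share. The figures do not show that the study's main result would be wrong. For chronic renal failure and end-stage renal disease the point is only a request for clarification.

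**What to change.** In the outcome list under Methods and in Statistical analysis:

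1. Run the complete/partial/no-response analyses in patients who do not already meet the complete-response definition at LN diagnosis, that is, with proteinuria of at least 0.5 g/24 h or eGFR not near normal. Define near-normal eGFR once and use it for both baseline and outcome.
2. Report the number set aside, and keep those patients for the other outcomes.
3. As a sensitivity analysis, repeat without patients whose eGFR was already reduced at biopsy, since those with fixed loss can meet neither response definition.
4. Include baseline proteinuria and eGFR in the multivariate models.
5. State that chronic renal failure and end-stage renal disease count only as new onset in patients free of each at biopsy.

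The cost is about one sentence per outcome. The baseline proteinuria and GFR are already on the collection list, and no treatment decision is affected. The downside is a slightly smaller denominator per outcome: for example 54 instead of 60 patients if 10% are set aside.

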## **EXPERIMENTAL STRATEGY AND RATIONALE**

In this project we will use renal biopsies from patients with LN. These samples, preserved in 10% formaldehyde and embedded in paraffin blocks by the corresponding Anatomic Pathology Services, correspond to patients with LN who underwent renal biopsies in the centers participating in the project.

BLYS (B lymphocyte stimulator) plays a key role in the pathophysiology of LN (14). Therefore, in this study we will focus on markers related to BLYS and its functional consequences. On the one hand, we will analyze among others the expression levels of BLYS and its receptors (BAFF-R, BCMA and TACI), since the expression levels of BLYS and its receptors are elevated in serum and renal biopsies of patients with LN and are associated with disease progression and severity (15-17).

On the other hand, because BLYS induces B cell survival (14), we will analyze the expression levels of different B cell markers such as CD19 and CD20 among others. Finally, we will analyze the plasma cell marker CD138, since plasma cell infiltration is associated with increased severity of lupus nephritis (18). We will analyze the expression levels of markers of other cell lineages such as CD3 for T cells and CD68 for macrophages.

We will also analyze at least 2 biomarkers whose urinary levels in patients with LN have been associated with a worse prognosis of LN: the chemokine MCP-1 (monocyte chemoattractant protein-1) and the enzyme NGAL (neutrophil gelatinase-associated lipocalin) (19).

The expression of these markers will be initially determined by immunohistochemical staining of renal biopsies, which are preserved in formaldehyde. The samples will be stained and analyzed mainly in the Anatomic Pathology Service of the “Complejo Hospitalario Universitario de Vigo” and in the laboratories of the “Instituto de Investigación Sanitaria Galicia Sur” (IISGS), although the different participating centers will participate in this work to the extent possible and cost-effective for the project. Different methods of quantification will be used in function of the stains of the different markers.

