#### Sample size

For this proof-of-concept study, our objective is to analyze around **60 renal biopsy** samples (expandable according to the results obtained).

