#### Methods:

The following **general variables** will be collected:

- demographic data: age, sex, ethnicity.
- clinical data on SLE:
  - diagnosis and chronological data: time of SLE diagnosis, time of LN diagnosis, time from SLE diagnosis to LN.
  - 1997 ACR SLE classification criteria,
  - activity: involvement of different organs and systems by SELENA-SLEDAI (10) at the time of LN diagnosis and at the time of the last evaluation of the patient (or death, if applicable).
  - damage: by item and by domain according to the Systemic Lupus International Collaborating Clinics Damage Index (SDI) (11) at the time of LN diagnosis and at the time of the last evaluation of the patient (or death, if applicable).
  - comorbidity: arterial hypertension, diabetes, dyslipemia, smoking habit, severe infections, neoplasms, etc. at the time of LN diagnosis and at the time of the last evaluation of the patient (or death, if applicable).
- laboratory data at the time of LN diagnosis and at the time of the last evaluation of the patient (or death, if applicable):
  - blood (general tests): acute phase reactants (erythrocyte sedimentation rate and C-reactive protein), full blood count, creatinin, glomerular filtration rate, blood urea nitrogen, liver function tests, lipid profile.

- blood (serological tests): complement (C3 and C4), levels of anti-dsDNA antibodies, antiphospholipid antibodies: anticardiolipin (Ig M and Ig G), anti-beta2GP-1 (Ig M and Ig G), lupus anticoagulant.
- urine: hematuria, piuria, proteinuria, casts.
- histopathological markers of renal biopsy:
  - histological class according to the 2003 ISN/RPS classification (9).
  - National Institutes of Health (NIH) activity index (12): score (maximum 24) and by item (endocapillary hypercellularity, neutrophils/karyorrhexis, hyaline deposits/wire loops, fibrinoid necrosis, cellular or fibrocellular crescents, interstitial inflammation).
  - National Institutes of Health (NIH) chronicity index (12): score (maximum 12) and by item (global glomerulosclerosis, fibrous crescents, tubular atrophy, interstitial fibrosis).
  - markers related to B lymphocytes which may include but is not limited to: CD19, CD20 and CD138.
  - markers related to BLYS (B lymphocyte stimulator) and its functional consequences which may include but is not limited to expression of BLYS and its receptors: BAFF-R, BCMA and TACI.

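### Source hospital is neither recorded nor used in any analysis, so hospital differences in staining and response could appear as marker-response associations; record it and report a centre-adjusted estimate beside the planned one

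*Combined protocol and SAP*

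**What the plan says.** The section on experimental strategy says that the samples "correspond to patients with LN who underwent renal biopsies in the centers participating in the project" and were "embedded in paraffin blocks by the corresponding Anatomic Pathology Services". The only handling detail common to all sites is 10% formaldehyde. Staining and reading are to be done mainly in Vigo, "although the different participating centers will participate in this work to the extent possible and cost-effective for the project". The ethics paragraph also implies several sites, since approval is to be sought "as well as from the CEIC of each center, if necessary".

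The list of general variables under Methods opens with "demographic data: age, sex, ethnicity" and goes on to disease history, laboratory results, histology, markers and treatments. The response and outcome variables follow. Biopsy hospital, treating hospital and fixation details appear in neither list.

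The statistical section splits patients by response, for example complete remission or not, and continues: "To establish differences between patients in these 2 groups, we will use the" chi-square or Fisher test, t-test or Mann-Whitney test. It then correlates staining with response and fits univariate and multivariate regressions on an open list of variable types. No centre term, stratum or random effect is named. The sample-size section says "our objective is to analyze around 60 renal biopsy samples (expandable according to the results obtained"), with no derivation. The number of centres is not stated in the text available to me.

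**The concern.** Staining is the exposure and renal response is the outcome. The hospital can influence the first through fixation and block storage, and the second through the patients it sees and how they are managed. A factor that acts on both sides of an association and is left out of the analysis can create an association where none exists within any hospital.

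This is a separate matter from which laboratory stains the slides. If every slide were stained and read in one place, local fixation would still differ, and so would local case mix and care.

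The project aims to find biopsy markers that predict response to treatment. A marker that mainly identifies the hospital would not do so elsewhere. If the hospital is not in the dataset, nobody can check afterwards.

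**Working it through.** **The plan's own figure.** The target of 60 cannot be reproduced, because no effect size, SD, response rate or power is given. For scale only: with a 30/30 split, power at a standardised difference d is Φ(d/√(2/30) − 1.96). At d = 0.73 this is Φ(2.83 − 1.96) = Φ(0.87), about 81%.

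**How the bias arises: two hospitals of 30, no marker effect within either.** Suppose staining is 1 within-hospital SD higher in hospital A, and response is 70% in A and 30% in B.
- Share of responders from A: 0.7/(0.7 + 0.3) = 0.7. Share of non-responders from A: 0.3/(0.3 + 0.7) = 0.3.
- Spurious difference: 1 × (0.7 − 0.3) = 0.40 SD.
- Overall SD: √(1 + 1² × 0.25) = 1.118. Standard error: 1.118 × √(2/30) = 0.289. Ratio: 0.40/0.289 = 1.39.
- Chance of p < 0.05: Φ(1.39 − 1.96) + Φ(−1.39 − 1.96), about 28%.

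With response 60% v 40% the spurious difference is 0.20 SD and the chance about 11%. With a staining shift of 0.5 SD the two chances are about 12% and 7%.

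**Several hospitals, by simulation.** From the plan: 60 biopsies, the pooled two-group test, and p < 0.05 (taken as two-sided). Assumed: 4 to 10 equal centres; staining = centre effect with SD sc plus within-centre error with SD 1; centre log-odds of response with SD sr; no association within centre. To read the assumptions:
- sc = 0.5 puts 0.25/1.25 = 20% of staining variance between hospitals; sc = 1.0 puts 1/2 = 50% there.
- Around a 50% response rate, hospitals one SD either side respond at 38% and 62% when sr = 0.5, and at 27% and 73% when sr = 1.0.

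False-positive rate of the pooled t-test:

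| sc, sr | 4 centres | 6 centres | 10 centres |
|---|---|---|---|
| 0.5, 0.5 | 6.4% | 5.9% | 5.9% |
| 0.5, 1.0 | 9.6% | 8.2% | 6.6% |
| 1.0, 1.0 | 16.7% | 13.6% | 10.0% |

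At sc = 0.33 and sr = 0.5 the rate is 5.0% to 5.8%. For the two rows with sr = 1.0, a linear model of marker on response plus centre gives 4.5% to 5.3%. With unequal centres (30, 12, 8, 6, 4) and sr = 1.0, the pooled rates are 8.6% (sc = 0.5) and 14.6% (sc = 1.0). A separate simulation with 3, 6 and 10 centres gave the same picture for the Mann-Whitney test. With only staining or only response varying by centre, the pooled rates there were 4.4% to 5.4%, which is no inflation.

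**What adjustment does to power** (true d = 0.736, pooled to adjusted):

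| Setting | 6 centres | 10 centres |
|---|---|---|
| Centres do not differ | 80% to 76% | 79% to 72% |
| Only response differs (sr = 1.0) | 77.5% to 67.1% | 79.3% to 64.3% |

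With 6 centres and both SDs at 0.5, power goes from 70% to 73%; with both at 1.0, from 54% to 67%. With 15 to 20 centres and no centre effects, adjustment loses about 12 to 18 points.

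**The case against.** **The inflation depends on the scenario.** The larger rates need a log-odds SD of 1.0, and the highest need half of the staining variance to lie between hospitals. At moderate values the pooled test is close to nominal, and the documents have no data on which case applies. This stands, and it is why the size must be given as a range. A reader might infer that the planned tests are invalid or that their results will be confounded. The documents support only that they could be and that the plan has no means of telling.

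**Case mix and care are partly measured.** Ethnicity, histological class, activity and chronicity indices, renal function, proteinuria and lupus nephritis treatment are all collected and could enter the multivariate model. This stands in part: no adjustment set is specified, and the pooled tests and correlations use none of these variables. None of them represents fixation. The common fixative and mainly central staining reduce technical variation but do not remove local differences in handling.

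**Adjustment is not free.** A reader might infer that a within-centre comparison should become the main analysis. The power figures do not support that while the number of centres is unknown. If only response differs by centre, adjustment loses roughly 10 points with 6 centres and 15 with 10, with no gain in error control. Where differences between hospitals reflect real disease severity, it also removes some true signal.

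**The treating hospital is an inference.** The text says where biopsies were taken, not who chose treatment. The two may coincide, but the plan does not say so.

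**The plan is exploratory.** It leaves room for further methods, so a centre term is permitted. But the choice would follow the observed results, and it needs a variable that is not listed.

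**Conclusion.** The point holds as a cheap improvement. Blocks were fixed locally at several centres, source hospital is not a listed variable, and no planned analysis uses it. Followed as written, the study could not separate a marker signal from a hospital signal, and for fixation no listed variable offers even partial control.

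The size is conditional. With 60 biopsies and an assumed 4 to 10 centres, the pooled false-positive rate is about 5% to 6% when the staining SD between centres is 0.5 or less of the within-centre SD and the log-odds SD is 0.5. It is about 7% to 17% when the log-odds SD is 1.0 and the staining SD is 0.5 to 1.0. Both dimensions must differ for any inflation to occur. The documents settle none of these inputs, so the figures show what is possible and do not estimate the bias in this study.

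**What to change.** 1. Under Methods, add source hospital (site of biopsy and fixation) to the general variables, and the treating hospital where it is different.
2. In the statistical section, keep the planned comparison. Add beside it, as a prespecified sensitivity analysis, a centre-adjusted estimate for each marker: a linear model of marker on response plus centre, with very small centres pooled into one stratum. Putting centre in a model for the marker avoids many centre terms in a logistic model with about 60 patients, which may be unstable.
3. Show each marker's distribution and the response rate by centre.
4. Describe a marker as associated with response only with the adjusted estimate reported alongside.

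Cost: one variable, which should be known for every block shipped, and one extra model per marker. The adjusted estimate is less precise. The loss is about 3 to 7 points of power with 4 to 10 centres that do not differ, about 9 to 16 if only response differs, and about 12 to 18 with 15 to 20 centres even without centre effects. For that reason it should accompany the planned analysis and not replace it.
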